4.2.1 Hematologic Dose Limiting Toxicity

Hematologic DLT is defined as follows:

- Grade 4 neutropenia lasting > 5 days
- \geq Grade 3 febrile neutropenia
- Grade 4 thrombocytopenia, irrespective of duration
- Grade 3 thrombocytopenia associated with clinically significant bleeding
- \geq Grade 3 hemolysis

The following events will be specifically excluded from the definition of hematologic DLT:

- \geq Grade 3 lymphopenia
- Grade 3 anemia that is not associated with other clinically significant complications.

4.2.2 Non-hematologic Dose Limiting Toxicity

- Any intolerable Grade 2 toxicity that results in dose interruption lasting more than 20 days, or requires drug withdrawal.
- Non-hematologic DLT is defined as any \geq Grade 3 non-hematologic event with the following exceptions:
 - Grade 3 electrolyte abnormality that lasts less than 72 hours, that is not otherwise associated with clinical complications, and responds to medical intervention
 - Grade 3 fever that lasts < 72 hours and is not associated with hemodynamic compromise
 - Grade 3 nausea or vomiting that lasts < 72 hours and responds to medical intervention
 - Grade 3 amylase and/or lipase elevation that is not associated with either clinical or radiographic evidence suggestive of pancreatitis.
 - Grade 3 gastrointestinal AEs of diarrhea, constipation, abdominal pain, cramping, dyspepsia or dysphagia that resolves to \leq Grade 1 within 14 days with medical therapy

- Grade 3 fatigue that lasts < 7 days
- Grade 3 infusion related reaction or cytokine release syndrome that lasts < 12 hours and responds to medical intervention.
- Grade 3 or 4 endocrinopathy that is adequately controlled with hormone supplementation
- Grade 3 skin toxicity that resolves to \leq Grade 2 within 14 days of initiation of corticosteroids
- Grade 3 inflammatory reaction (e.g., with associated pain, swelling) attributed to a local antitumor response (e.g., inflammatory reaction at sites of metastatic disease, lymph nodes, etc.) that resolves to \leq Grade 2 within 7 days.

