4.2 Dose Limiting Toxicity (Tebotelimab Cohort)

For the purposes of safety management and defining DLTs, the combination of enoblituzumab + tebotelimab will be treated as one entity. If a DLT is considered related to study treatment, no distinction will be made as to which agent is the causative agent and administration of both agents will be stopped.

Dose limiting toxicities will be based on treatment-emergent drug-related AEs (or laboratory abnormalities) occurring through Cycle 2 Day 7.

Patients in the Tebotelimab Cohort who experience DLT will discontinue study treatment.

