4.2.3 Hepatic Non-hematologic Dose Limiting Toxicity

Hepatic non-hematologic DLT will be defined as follows:

- Any elevation of one or more transaminases $> 8 \times$ the institutional upper limit of normal (ULN) irrespective of duration.
- Any Grade 3 elevation of one or more transaminases $> 5.0 - 8.0 \times$ the ULN that does not resolve to Grade 2 within 7 days, and Grade 1 or baseline within 14 days. If steroids are administered, they must be tapered to ≤ 10 mg of prednisone or equivalent per day by Day 14. Please see [Section 7.2.2](#) for further management guidelines.
 - For patients with Grade 1 or 2 elevations of transaminases at baseline, a doubling of transaminases will be considered dose limiting, if not resolved to baseline within 14 days.
- Any Grade 3 elevation of total bilirubin that is $> 5 \times$ the ULN irrespective of duration.
- Any elevation of total bilirubin $> 3.0 - 5.0 \times$ ULN that does not resolve to Grade 2 within 7 days and Grade 1 or baseline within 14 days. If steroids are administered, they must be tapered to ≤ 10 mg of prednisone or equivalent per day by Day 14. Please see [Section 7.2.2](#) for further management guidelines.
- Any event meeting the criteria for Hy's law as follows (all three features):
 - Aspartate aminotransferase (AST) and/or alanine aminotransferase (ALT) $> 3 \times$ ULN, or doubling of AST and/or ALT for patient having Grade 2 transaminase levels at baseline.
 - Concurrent elevation of total bilirubin $> 2 \times$ ULN without initial evidence of cholestasis
 - No alternative etiology can be identified.

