4.3.1 Dose Delays

Tebotelimab Cohort

Patients who experience a Grade 2 to 4 AE that is potentially dose-limiting should have study drug held pending assessment, management, and resolution of the AE. If the AE is assessed as unrelated to study drug or does not meet DLT criteria, therapy may be restarted at the previous dose and schedule, after appropriate recovery.

Retifanlimab and Tebotelimab Cohorts

A dose delay of up to 20 days is allowed for patients experiencing AEs. In the case of abnormal troponins or N-terminal pro b-type natriuretic peptide (NT-proBNP) values, study drug must be withheld and a thorough cardiac assessment performed promptly to diagnose myocarditis or other cardiovascular diseases; the patient may resume study drugs if myocarditis is not confirmed. Refer to [Section 7](#) for specific guidance on restarting study therapy for IRR and irAEs. A dose delay of up to 20 days may also be permitted for reasons other than AEs. All procedures at the missed dosing visit should be performed and treatment reinstated as if the delay had not occurred.

Patients with infusion delays > 20 days will discontinue the study drug, complete the End of Treatment visit, and then enter the Post-treatment Follow-up Period.

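### Section 4.2.2 has no hepatic exception, so a lower-band Grade 3 liver test rise that resolves on time is a DLT there but not under Section 4.2.3

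*Protocol*

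**What the plan says.** Section 4.2 bases DLTs on drug-related adverse events or laboratory abnormalities through Cycle 2 Day 7. The consequence is fixed: "Patients in the Tebotelimab Cohort who experience DLT will discontinue study treatment".

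Section 4.2.2 first makes a DLT of an intolerable Grade 2 toxicity that leads to a long interruption or to drug withdrawal. It then counts anything at or above a "Grade 3 non-hematologic event with the following exceptions". The ten exceptions cover electrolytes, fever, nausea or vomiting, amylase or lipase, other gastrointestinal events, fatigue, infusion reactions or cytokine release, endocrinopathy, skin, and local inflammatory reactions. None concerns transaminases or bilirubin, and none points to Section 4.2.3.

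Section 4.2.3 opens with "Hepatic non-hematologic DLT will be defined as follows". For transaminases in the band above 5 and up to 8 x ULN, a Grade 3 rise counts only if it "does not resolve to Grade 2 within 7 days, and Grade 1 or baseline within 14 days". Bilirubin above 3 and up to 5 x ULN has the same time limits. Both bullets add a steroid condition ("If steroids are administered, they must be tapered to" 10 mg or less of prednisone per day by Day 14). For patients who enter with Grade 1 or 2 transaminases, "a doubling of transaminases will be considered dose limiting, if not resolved to baseline within 14 days". Hy's law cases always count.

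Under Section 4.3.1, patients with a potentially dose-limiting event "should have study drug held pending assessment, management, and resolution of the AE", and may restart if the event proves unrelated or is not a DLT. Section 7.2.2 allows treatment to resume after lower-band Grade 3 liver rises on the same 7-day, 14-day and taper conditions.

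**The concern.** Section 4.2.2 is written as a general rule with a closed list of exceptions, and Section 4.2.3 labels its events a kind of non-hematologic DLT. Neither section says which prevails. A site that applies 4.2.2 as written would permanently stop a patient whom 4.2.3 and 7.2.2 allow to continue, and would report one more DLT. Section 4.3.1 does not settle the matter: for a drug-related event it makes restart depend on whether the DLT criteria are met, which is the question in dispute.

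The DLT count in the first 12 Tebotelimab Cohort patients informs the choice between 600 mg, 300 mg and termination (Section 4.1), and safety is part of that cohort's primary objective (Section 3.1). With about 35 centers, one event should have one classification.

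**Working it through.** The plan gives no figure for this point, so the check is a comparison of texts followed by a rough scale.

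**Are laboratory rises within 4.2.2?** Yes. Section 4.2 names laboratory abnormalities, and 4.2.2 needs an exception for "Grade 3 amylase and/or lipase elevation that is not associated with either clinical or radiographic evidence suggestive of pancreatitis". Section 7.2.2.2 places bilirubin above 3 and up to 5 x ULN under Grade 3, so the lower bilirubin band meets the 4.2.2 threshold.

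**Test cases** (drug-related, within the DLT window, each section read literally):

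| Event | 4.2.2 | 4.2.3 |
|---|---|---|
| Transaminases 6 x ULN, Grade 2 by day 7, Grade 1 by day 14, steroids tapered by Day 14, no doubling or Hy's law criterion met | DLT | Not a DLT |
| Bilirubin 4 x ULN, same course | DLT | Not a DLT |
| Either of these, not resolved or not tapered in time | DLT | DLT |
| Transaminases above 8 x ULN | DLT | DLT |
| Bilirubin above 5 x ULN, Grade 3 | DLT | DLT |
| Bilirubin Grade 4 | DLT | Not reached by the bilirubin bullets, because the one above 5 x ULN is limited to Grade 3 |
| Intolerable Grade 2 liver rise requiring withdrawal | DLT | Not a DLT unless doubling or Hy's law applies |

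The first two rows are the conflict. The last two show events that only 4.2.2 clearly catches, and these limit how the fix may be worded.

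**Scale.** The documents give no rate for the disputed event. The nearest figures are in Section 2.3.4.2. In tebotelimab monotherapy dose escalation (53 patients), related Grade 3 or higher events included one immune-mediated hepatitis and one transaminases increased. These may be one patient or two.

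- One patient: 1/53 = 1.9% (exact 95% CI 0.05% to 10.1%). Expected in 12: 12 x 1/53 = 0.23.
- Two patients: 2/53 = 3.8% (exact 95% CI 0.46% to 13.0%). Expected in 12: 12 x 2/53 = 0.45.
- Highest upper limit: 12 x 0.130 = 1.6 patients.
- Chance of two or more in 12, from 1 - (1-p)^12 - 12p(1-p)^11: 2% at p = 1/53 and 7% at p = 2/53.

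These figures are before requiring the lower band, onset by Cycle 2 Day 7, timely resolution and taper, each of which reduces them. In the other direction, they come from monotherapy at mixed doses in mixed tumors, and the rate with enoblituzumab is not given. Section 5.1 also admits patients with hepatic metastases and ALT or AST up to 5 x ULN, directly below the disputed transaminase band.

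**Effect of one such patient.** The DLT count changes by 1/6 = 16.7 percentage points in a mini-cohort, or 1/12 = 8.3 points overall. The window is 21 + 7 = 28 days, so the patient would stop after at most two doses.

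**The case against.** The strongest reply is that the intended reading is clear. Section 4.2.3 is a dedicated hepatic definition that refers to 7.2.2, and its time and taper conditions match those for resuming. If 4.2.2 governed, the threshold bullets of 4.2.3 would have almost nothing to add. Most readers would apply 4.2.3. That stands, and it makes this a drafting conflict rather than a flaw in the intended design.

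The sponsor would also usually be involved early. Immune-related hepatitis of Grade 2 or higher is reportable within 24 hours (Table 5). Steroids for suspected immune-related events are used in consultation with the Medical Monitor (Section 8.1.1). The sponsor must be alerted within 24 hours of a decision to withdraw a patient from dosing (Section 4.4). An unnoticed misclassification is therefore unlikely. These are routes for discussion, however, and none states which definition applies.

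Two stronger readings are tempting. A reader might infer that the conflict could by itself trigger dose reduction or closure of the cohort. The documents do not support that: Section 4.1 states no numeric DLT threshold, and action follows an ad hoc meeting if warranted. A reader might also infer that the two sections differ only on resolved lower-band rises, so that hepatic events could simply be handed over to 4.2.3. The last two rows of the table show otherwise. That wording could remove intolerable Grade 2 liver toxicity and, read literally, Grade 4 bilirubin outside Hy's law from the DLT definition.

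**Conclusion.** The point holds as a conflict in the text of an operative safety rule, and it should be corrected. One well-defined group of events, resolved lower-band Grade 3 transaminase or bilirubin rises, is a DLT with mandatory discontinuation under 4.2.2 and not a DLT under 4.2.3. Section 4.2.3 is probably meant to govern.

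The likely extent is 0 or 1 run-in patient. That rests on the assumption that the monotherapy experience indicates the order of magnitude for the combination. The literal reading of 4.2.2 errs toward stopping treatment, so it does not under-protect patients. Its cost is an unnecessary discontinuation and an inflated DLT count. Sample size and the efficacy analyses are not affected.

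**What to change.** 1. Add one exception to the Grade 3 or higher bullet of Section 4.2.2: *Grade 3 transaminase elevation >5.0-8.0 x ULN or total bilirubin elevation >3.0-5.0 x ULN that meets the resolution and steroid-taper conditions of Section 4.2.3 and meets no other criterion in 4.2.3 (baseline doubling, Hy's law).*
2. Leave the intolerable Grade 2 bullet of 4.2.2 in force for hepatic events.
3. In the 4.2.3 bullet on total bilirubin above 5 x ULN, delete the limitation to Grade 3, so that any elevation above that level counts and Grade 4 is clearly included.

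The cost is one added line and one deleted phrase in the protocol. Visits, sample size and analyses do not change.

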4.2.3 Hepatic Non-hematologic Dose Limiting Toxicity

Hepatic non-hematologic DLT will be defined as follows:

- Any elevation of one or more transaminases $> 8 \times$ the institutional upper limit of normal (ULN) irrespective of duration.
- Any Grade 3 elevation of one or more transaminases $> 5.0 - 8.0 \times$ the ULN that does not resolve to Grade 2 within 7 days, and Grade 1 or baseline within 14 days. If steroids are administered, they must be tapered to ≤ 10 mg of prednisone or equivalent per day by Day 14. Please see [Section 7.2.2](#) for further management guidelines.
 - For patients with Grade 1 or 2 elevations of transaminases at baseline, a doubling of transaminases will be considered dose limiting, if not resolved to baseline within 14 days.
- Any Grade 3 elevation of total bilirubin that is $> 5 \times$ the ULN irrespective of duration.
- Any elevation of total bilirubin $> 3.0 - 5.0 \times$ ULN that does not resolve to Grade 2 within 7 days and Grade 1 or baseline within 14 days. If steroids are administered, they must be tapered to ≤ 10 mg of prednisone or equivalent per day by Day 14. Please see [Section 7.2.2](#) for further management guidelines.
- Any event meeting the criteria for Hy's law as follows (all three features):
 - Aspartate aminotransferase (AST) and/or alanine aminotransferase (ALT) $> 3 \times$ ULN, or doubling of AST and/or ALT for patient having Grade 2 transaminase levels at baseline.
 - Concurrent elevation of total bilirubin $> 2 \times$ ULN without initial evidence of cholestasis
 - No alternative etiology can be identified.

4.3 Guidelines for Dose Modification

No inpatient reductions in the dose of enoblituzumab, retifanlimab, or tebotelimab are allowed. Dose interruption or discontinuation should be used for the management of drug-related toxicity. The management of IRR is specified in [Section 7.1.3](#). The management of immune-related AEs (irAEs) is specified in [Section 7.2](#).

4.3.1 Dose Delays

Tebotelimab Cohort

Patients who experience a Grade 2 to 4 AE that is potentially dose-limiting should have study drug held pending assessment, management, and resolution of the AE. If the AE is assessed as unrelated to study drug or does not meet DLT criteria, therapy may be restarted at the previous dose and schedule, after appropriate recovery.

Retifanlimab and Tebotelimab Cohorts

A dose delay of up to 20 days is allowed for patients experiencing AEs. In the case of abnormal troponins or N-terminal pro b-type natriuretic peptide (NT-proBNP) values, study drug must be withheld and a thorough cardiac assessment performed promptly to diagnose myocarditis or other cardiovascular diseases; the patient may resume study drugs if myocarditis is not confirmed. Refer to [Section 7](#) for specific guidance on restarting study therapy for IRR and irAEs. A dose delay of up to 20 days may also be permitted for reasons other than AEs. All procedures at the missed dosing visit should be performed and treatment reinstated as if the delay had not occurred.

Patients with infusion delays > 20 days will discontinue the study drug, complete the End of Treatment visit, and then enter the Post-treatment Follow-up Period.

4.4 Study Treatment Discontinuation

Patients who tolerate treatment may continue to receive treatment with the study drug(s) as specified in the protocol until any one of the following conditions are met:

- Adverse Event Requiring Treatment Discontinuation
 - Patients who discontinue study treatment due to AEs are followed by radiographic evaluation until disease progression by RECIST v1.1, if the patients' condition allows. If not, patients will be followed for OS without radiographic evaluation upon the discussion with the Sponsor's Medical Monitor.
- Completed Treatment per Protocol
- Death
- Physician Decision (should occur only after discussion with the Sponsor's Medical Monitor)

- Lost to Follow-up
- Pregnancy
- Progressive Disease-Clinical Progression
- Progressive Disease-Objective Progression
 - Patients who have radiographic progression according to RECIST v1.1 may remain on study treatment until the next scheduled radiographic evaluation if the following conditions are met:
 - Absence of clinical symptoms or signs indicating clinically significant disease progression.
 - No decline in ECOG performance status.
 - Absence of rapid disease progression or threat to vital organs or critical anatomical sites (e.g., CNS metastasis, respiratory failure due to tumor compression, spinal cord compression) requiring urgent alternative medical intervention.
 - No significant, unacceptable, or irreversible toxicities related to study treatment.
- Major Protocol Deviation Requiring Treatment Discontinuation
- Study Terminated (patients might be offered enrollment in a follow-up/roll over protocol if in place at the time of study termination)
- Patient Decision
- Patient Withdrew Consent for Study

If the Investigator decides that the patient should be withdrawn from the study or from dosing for any reason other than disease progression, the Sponsor or its designee must be alerted within 24 hours).

A patient may be determined to be lost to follow up (LTFU) after there have been 3 documented phone contact attempts. If this fails, a certified letter should be sent to the patient. Only after these attempts have failed can a patient be determined to be LTFU.

4.5 Study Discontinuation

Patients who are no longer on treatment but are still followed on the study can be terminated from the study for the following reasons:

- Completed Protocol-Defined Follow-up Period
- Death

- Lost to Follow-up
- Study Terminated by Sponsor
- Patient withdrew from Study

4.6 Definition of End of Study

The end of study will occur after the last patient has met off-study criteria and the data collection process is completed (time of study database lock).

End of study for each patient is defined as follows: Patient is LTFU or discontinues from the study due to any reason. Each patient's end of study status will be recorded in the End of Study CRF page.

5 ELIGIBILITY CRITERIA

To be eligible for study participation, patients must meet all the inclusion criteria. Patients will be excluded from the study if they meet any exclusion criteria. No exceptions to these criteria will be granted by the Sponsor.

5.1 Inclusion Criteria

1. Ability to provide informed consent and documentation of informed consent prior to initiation of any study-related tests or procedures that are not part of standard of care for the patient's disease.
2. Age \geq 18 years old.
3. Histologically proven, recurrent or metastatic SCCHN not curable by local therapy.
4. No prior systemic therapy for SCCHN in the recurrent or metastatic setting (with the exception of systemic therapy completed $>$ 6 months prior if given as part of multimodal treatment for locally advanced disease).
5. Primary tumor locations of oropharynx, oral cavity, hypopharynx, or larynx. Patients may not have a primary tumor site of upper esophagus, salivary gland, or nasopharynx (any histology).
6. All patients enrolled in this study must have an identified formalin-fixed, paraffin embedded (FFPE) tumor specimen for immunohistochemical evaluation of pharmacodynamic markers of interest. If no archival specimen is available, tissue from a contemporaneous core or excisional biopsy is acceptable (fine needle aspirate is not sufficient; refer to [Section 9.9.3](#) for details).

Patients must also be willing to provide consent for a baseline and on-treatment tumor biopsy, if tumor lesions are accessible for biopsy with acceptable risk in the judgment of the Investigator and after discussion with the Sponsor (refer to [Section 9.9.3](#) for details). This requirement will expire after an adequate number of samples have been collected, as determined by the Sponsor.

7. Eastern Cooperative Oncology Group (ECOG) performance status of 0 or 1, verified within 3 days before Day 1.
8. Life expectancy \geq 6 months.
9. Has adequate end organ function as determined by the site Investigator.
10. Has at least one radiographically measurable lesion (target lesion), as defined in RECIST v1.1 and documented by computed tomography (CT) or magnetic resonance imaging (MRI), suitable for response monitoring.
11. Has PD-L1 expression level that is either:
 - a. Positive (CPS \geq 1) for the **Retifanlimab Cohort**, or
 - b. Negative (CPS $<$ 1) for the **Tebotelimab Cohort**
12. Has results from testing of HPV p16 status for oropharyngeal cancer.

13. Acceptable laboratory parameters as follows:
 - a. Platelet count $\geq 100 \times 10^3/\mu\text{L}$ without transfusion within 28 days prior to the initiation of study drug.
 - b. Absolute neutrophil count $\geq 1.5 \times 10^3/\mu\text{L}$ in the absence of any growth factor support within 28 days prior to the initiation of study drug.
 - c. ALT/AST $\leq 2.5 \times \text{ULN}$; for patients with hepatic metastases, ALT and AST $\leq 5 \times \text{ULN}$.
 - d. Total bilirubin $< 1.5 \times \text{ULN}$, except patients with Gilbert's syndrome, who may enroll if the conjugated bilirubin is within normal limits.
 - e. Creatinine $< 2 \text{ mg/dL}$, or a calculated or measured creatinine clearance $> 50 \text{ mL/min}$.
 - f. Negative serum pregnancy test, if applicable.
14. Women patients of child-bearing potential (WOCBP), defined as not surgically sterilized (hysterectomy, bilateral salpingectomy, and bilateral oophorectomy) and between menarche and 1-year post menopause, must have a negative serum pregnancy test performed within 72 hours prior to the initiation of study drug administration. Female patients must agree to abstain from egg donation during the course of the study.
15. WOCBP and male patients with partners of WOCBP must agree to use highly effective methods of contraception according to [Section 8.1.3](#) from the time of consent through 120 days after discontinuation of study drug administration. Male patients must agree to abstain from sperm donation during the course of the study.
16. WOCBP is not pregnant or breastfeeding or male patient is not expecting to father children within the projected duration of the study, starting with screening visit through 120 days after the last dose of study drug.

